If your application involves the use of a HUD "humanitarian" device: describe whether the use is for "on-label" clinical patient care, "off-label" clinical patient care, and/or research (collecting safety and/or effectiveness data).

The purpose of this study is to explore the effectiveness of interventions that may be useful during aeromedical evacuation (AE) or prolonged filed care (PFC).

Skin cellular injury, skin perfusion, and skin microclimate will be tested with and without Mepilex sacral dressing or LiquiCell pads on 3 transport surfaces. Note: A litter is a stretcher.

Aeromedical Evacuation (AE) conditions

- Mepilex: Litter + AE mattress + 30° backrest
- Without Mepilex: Litter + AE mattress + 30° backrest
- Mepilex: Vacuum Spine Board (VSB) placed on AE mattress
- Without Mepilex: Vacuum Spine Board (VSB) placed on AE mattress

Prolonged Field Care (PFC) conditions

- LiquiCell: Talon Litter
- Without LiquiCell: Talon Litter

Aim 1. Under conditions simulating aeromedical evacuation (stretcher + mattress or stretcher + mattress + vacuum spine board) compare the effects of with/without Mepilex (multilayered dressing) on the buttocks/lower back (sacrum) on indicators of skin injury, skin blood flow and oxygenation, skin temperature and moisture and pressure between the support surface and the skin (interface pressure).

Aim 2. Under conditions simulating prolonged field care (field stretcher without a mattress pad) evaluate the effect of with/without LiquiCell (a pad with fluid-filled pocked of liquid) placed under the back and bottom on indictors of skin injury, blood flow, oxygenation, temperature, moisture and interface pressure.

(1.6) Study design. Provide a one-sentence description of the general study design and/or type of methodology.

Your answer will help HSD in assigning applications to reviewers and in managing workload. Examples: a longitudinal observational study; a double-blind, placebo-controlled randomized study; ethnographic interviews; web scraping from a convenience sample of blogs; medical record review; coordinating center for a multi-site study.

Stratified randomized control trial with subjects assigned to either the AE or Prolonged Field Care arms with or without the intervention. Stratification will be based on body fat percentage.

(1.7) Intent. Check all the descriptors that apply to your activity. You must place an "X" in at least one box.

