5 PROCEDURES

5.1 Study procedures. Using lay language, provide a complete description of the study procedures, including the sequence, intervention or manipulation (if any), drug dosing information (if any), use of records, time required, and setting/location. If it is available and you think it would be helpful to the IRB: Upload a study flow sheet or table to the **Supporting Documents** SmartForm in **Zipline**.

For studies comparing standards of care: It is important to accurately identify the research procedures. See UW IRB POLICY:
Risks of Harm from Standard Care and the draft guidance from the federal Office of Human Research Protections, "Guidance on Disclosing Reasonably Foreseeable Risks in Research Evaluating Standards of Care"; October 20, 2014.

Researcher Date & Version

The study will take place in a temperature-controlled room (~72°F) at the University of Washington School of Nursing. Subjects will be assigned to one of six groups. Each subject will be clothed in a single layer of cotton like clothing (scrubs) and undergarments and socks. Height and weight will be obtained using a standup calibrated device and body fat will be measured using the InBody 570 Body Composition Analyzer. This device is used for medical research and in health clubs and involves standing on a scale.

Group Assignment: Subjects will first be stratified based on body fat percentage (< 10%, 10%-20%; > 20%). Using close block stratification, subjects will be randomly assigned to one of six groups to ensure distribution based on body composition.

Aeromedical Evacuation (AE) conditions

- Group 1: Mepilex: Litter + AE mattress + 30° backrest
- Group 2: Without Mepilex: Litter + AE mattress + 30° backrest
- Group 3: Mepilex: Vacuum Spine Board (VSB) placed on AE mattress
- Group 4: Without Mepilex: Vacuum Spine Board (VSB) placed on AE mattress

Prolonged Field Care (PFC) conditions

- Group 5: LiquiCell: Talon Litter
- Group 6: Without LiquiCell: Talon Litter

All Groups

[figure not shown]
Acclimation: All subjects will complete a 20-minute acclimation period in the study room.

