As outlined in section 5.1 the following variables will be obtained: Height, weight, gender, percent body fat. Physiological variables that will be collected either continuously or intermittently include transcutaneous tissue oxygen on sacrum/chest, skin temperature on sacrum, skin moisture on sacrum, IL-1 (cytokine) obtained from epidermis of sacrum. We will also measure skin interface pressure on the buttocks/sacrum and subjects report of comfort/discomfort will be obtained every 30 minutes during the supine position.

(5.4) Data sources. For all types of data that you will access or collect for this research: Identify whether you are obtaining the data from the subjects (or subjects' specimens) or whether you are obtaining the data from some other source (and identify the source).

If you have already provided this information in Question 5.1, you do not need to repeat the information here.

Only the data outlined in the study procedures will be used in this study (height, weight, gender, body fat, skin oxygenation, skin temperature, skin moisture, cytokines from epidermis, skin interface pressure).

5.5 Retrospective/prospective. For all types of data and specimens that you will access or collect for this research: do all data and specimens to be used in the research exist (for example, in subjects' medical records) at the time this application is being submitted for initial review?

	х	No
		Yes
Include any necessary comments or explanation below (Note that for most studies this can be left blank)		

5.6 Identifiability of data and specimens. Answer these questions carefully and completely. This will allow HSD to accurately determine the type of review that is required and to assist you in identifying relevant compliance requirements. Review the following definitions before answering the questions:

Access means to view or perceive data, but not to possess or record it. See, in contrast, the definition of "obtain". Identifiable means that the identity of an individual is or may be readily (1) ascertained by the researcher or any other member of the study team from specific data variables or from a combination of data variables, or (2) associated with the information.

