## Cover

**Official Title of Study**: Prevention of Pressure Injuries During Aeromedical Evacuation or Prolonged Field Care

#NCT03924622

Date: 4 Jan 2019

Statistical Analysis Plan This study proposes to compare the effect of presence or absence of a Mepilex dressing) on variables (IL- $1\alpha$ /TP, TcPO2, interface pressure, skin temperature and moisture) potentially reflecting the modified effects of pressure, shear and microclimate associated with lying for an interval of (120 minutes) on either a standard NATO litter with mattress or a VSB. Primary analyses will contrast the Mepilex and non-Mepilex dressing groups, WITHIN the two support platform strata. That is, the two contrasts LITTER + Mattress (Mepilex vs. not) and VSB (Mepilex vs. not) will be the analysis foci. Analyses of the effect of support platform, and the interactions of platform with presence/absence of Mepilex pad will be considered secondary and exploratory. The statistical tests will be based on a group (Mepilex vs. non-Mepilex) by time (first sample – unloaded baseline, second sample post 120-minute loading) analysis. Analysis options depending on data structure include a repeated measures Group x Time ANOVA, an ANCOVA-based group analysis of the post-loading measurement controlled for the preloading measurement, a group analysis of the simple change score (post-loading – preloading), and a longitudinal analysis of the two-time points by group using Generalized Estimating Equations or a Linear Mixed Models. It is important to note that several of the studies using IL-1 $\alpha$  as a dependent variable have used non-parametric statistical tests. Similarly, error bar plots in published papers document a degree of heteroscedasticity, with the variability in a batch apparently having considerable dependence on its mean. This potential non-normality problem may be met with data transformation (e.g., square root or logarithmic transform) to an appropriate carrier or use of Generalized Linear Models with an appropriate non-linear monotonic link function, or the use of non-parametric statistics. As an example of application of the last method to the current data structures, the simple change score or residual change score from pre- to post- loading could be analyzed with the non-parametric Mann-Whitney U test. Power Analysis: The a priori justification of group sample size with respect to statistical power will be based on the potential change in the variable (IL- $1\alpha$ /Total ratio), which is measured in each participant immediately before and after lying for 120 minutes on the support platform. The analyses of other variables (e.g., TCPO2, interface pressure, skin temperature/moisture) will be treated as descriptive and secondary. When there is limited evidence in the literature that bear directly on the estimation of an effect size in planning a preliminary study, several authors and agencies have argued for setting the sample size per group N per group = 12.76-78 Assuming two tailed two independent group comparisons, with an adjusted significance threshold set to alpha = 0.025 to accommodate multiple testing at the alpha = 0.05 level for both the NATO litter and the "VSB" strata, and the size of each group N = 12, the minimum Cohen's d effect size per test necessary to achieve statistical power P = 0.80 is d = 1.336, which is considered a very large and ambitious effect size. However, there is related support in the literature that this level of effect is achievable using the proposed protocol. Hemmes55 (see Fig. 3, page 86, and Table A1, page 88) demonstrated that lying on either a rigid or soft-layered spineboard for 60 minutes raised mean sacral IL- $1\alpha$ /TP ratio by more than a factor of 10. de Wert24 (see Fig. 4A, page 510), using a 30- minute pressure and shear loading protocol on the forearm, showed that the presence of a Mepilex dressing resulted in IL-1 $\alpha$ /TP ratio levels that were on the order of 7 times smaller than the "no dressing" condition.

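### Randomisation is stratified by body-fat percentage, but no analysis named in the SAP includes it, so a possible gain in precision is forgone in the model-based contrasts

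*Protocol*

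**What the plan says.** Protocol section 1.6 describes a stratified randomised trial and states: "Stratification will be based on body fat percentage". Section 5.1 (Group Assignment) gives three strata, below 10%, 10% to 20% and above 20% body fat, and continues: "Using close block stratification, subjects will be randomly assigned to one of six groups to ensure distribution based on body composition". Section 5.3 confirms that the measurement is kept as data: "the following variables will be obtained: Height, weight, gender, percent body fat".

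The SAP sets the primary contrasts, Mepilex against no Mepilex, "WITHIN the two support platform strata". Strata there means litter plus mattress or vacuum spine board, not body fat. The candidate methods follow: "Analysis options depending on data structure include a repeated measures Group x Time ANOVA", then "an ANCOVA-based group analysis of the post-loading measurement controlled for the preloading measurement", a change-score comparison, and GEE or a linear mixed model. For non-normal data it adds transformation, generalized linear models and Mann-Whitney. Body fat appears in none of them. The power statement is for a plain two-group comparison: "statistical power P = 0.80 is d = 1.336, which is considered a very large and ambitious effect size".

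**The concern.** Stratified allocation removes chance differences in body fat between the two arms of a contrast. If the model then leaves body fat out, any outcome variation it causes stays in the error term, although it no longer contributes to the sampling error of the group difference. The standard error is overstated, the test rejects too rarely under the null, and the interval is wider than it need be.

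With 12 subjects per group, and a required effect that the SAP itself regards as ambitious, any precision available from data already collected is worth having. What is at stake is power and interval width. The validity of the test is not in question.

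**Working it through.** **Inputs.** From the SAP: 12 per group, two-sided alpha 0.025 per contrast, power 0.80, d = 1.336. From Protocol 5.1: three body-fat strata. Not in the documents and therefore assumed: R², the share of variance in the analysed outcome that body fat explains. For the ANCOVA this means the share left after the pre-loading value. The range used is 0, 0.05, 0.10 and 0.20.

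**1. The SAP's own figure.** For a two-sample t test, df = 2 × 12 − 2 = 22 and the noncentrality is d√(n/2) = 1.336 × √6 = 3.273. Two-sided alpha 0.025 gives power 0.79997, and solving for power 0.80 gives d = 1.336. The figure reproduces.

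**2. Closed-form check with the stratum as a factor (2 df).** Now df = 20 and the noncentrality is d√(n/2)/√(1 − R²). At R² = 0.10 this is 3.273/√0.90 = 3.450. Power at d = 1.336 is 0.795, 0.816, 0.838 and 0.882 at R² = 0, 0.05, 0.10 and 0.20. The detectable d is 1.344, 1.310, 1.275 and 1.203.

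**3. Simulation of the proposed remedy: one continuous body-fat term.** 60,000 contrasts per setting (Monte Carlo SE about 0.0017 for power, 0.0006 for level). Assumed: 1, 5 and 6 subjects per arm in the three strata; body fat normal with mean 20 and SD 7 within strata limits; a linear effect; ANCOVA pre-loading slope 0.5; d in SD units of the outcome analysed.

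| Assumed R² | ANCOVA power, without → with | ANCOVA level without body fat | ANCOVA interval width | Change-score power, without → with |
|---|---|---|---|---|
| 0 | 0.776 → 0.767 | 0.025 | +1.0% | 0.803 → 0.794 |
| 0.05 | 0.781 → 0.792 | 0.023 | −1.8% | 0.805 → 0.817 |
| 0.10 | 0.782 → 0.814 | 0.020 | −4.5% | 0.806 → 0.836 |
| 0.20 | 0.787 → 0.860 | 0.016 | −10.3% | 0.812 → 0.880 |

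The ANCOVA starts at 0.776 rather than 0.80 because the pre-loading slope has to be estimated. With body fat in the model the level is 0.025 (ANCOVA) and 0.025 to 0.026 (change score). Break-even R² is about 0.02 for the change score and 0.025 for the ANCOVA.

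**4. Which effect of body fat matters.** With two time points, the Group × Time test and the change-score test give the same t. In one simulated data set both gave 0.983 on 22 df, and with body fat (entered as body fat × time in the former) both gave 0.963 on 21 df. A stable effect of body fat on the marker's level cancels in the change, so only an effect on the response to loading counts. In the ANCOVA, a stable level effect leaves a remainder whenever the pre-loading slope is below 1:

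partial R² = r²(1 − ρ)² / [(1 − ρ²)(1 − r²)],

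where r² is the share of level variance explained and ρ the pre-post correlation. With r² = 0.20 and ρ = 0.5 this is 0.20 × 0.25 / (0.75 × 0.80) = 0.083.

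| ρ (r² = 0.20) | Partial R² | ANCOVA power, without → with |
|---|---|---|
| 0.3 | 0.135 | 0.785 → 0.828 |
| 0.5 | 0.083 | 0.785 → 0.807 |
| 0.8 | 0.028 | 0.780 → 0.781 |

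The change score gains nothing in this case (0.801 → 0.795).

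**5. Sensitivity, at R² = 0 / 0.05 / 0.10 / 0.20.**
- True effect a step at 20% body fat, linear term fitted (ANCOVA): 0.778 → 0.769 / 0.776 → 0.779 / 0.782 → 0.798 / 0.795 → 0.833.
- Log-normal marker (log SD 0.5) analysed untransformed: 0.671 → 0.660 / 0.670 → 0.679 / 0.667 → 0.697 / 0.669 → 0.742.
- Mann-Whitney, plain against adjusted: 0.741 against 0.712 at R² = 0, and 0.746 against 0.751 at 0.10.

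**6. Expressed in subjects.** Unadjusted ANCOVA power is 0.776, 0.817 and 0.852 with 12, 13 and 14 per group. At R² = 0.10 the gain is 0.814 − 0.782 = 3.2 points, against 0.817 − 0.776 = 4.1 points for one more per group: roughly 0.8 of a subject. At 0.20 it is 7.3 points against 7.6 for two more.

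**The case against.** The strongest reply is that nothing here is an error. Section 5.1 gives stratification one purpose, an even spread of body composition, and the design achieves it without adjustment. No text promises an adjusted analysis, the level is not inflated, and the SAP's list of methods is open enough to admit a covariate. All of that is correct, and it is why the point ranks as minor.

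The benefit also rests on an R² that the documents do not supply, and its sign changes within the range shown: a loss of about one point at zero, little at 0.05, and a clear gain only from about 0.10. Under a step effect, or a stable level effect with high pre-post correlation, the gain is smaller or absent. This stands too. What remains is the asymmetry: about one point at risk, against three to seven points if body fat explains 10% to 20%.

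The SAP also follows its remark about an ambitious effect by citing roughly 7-fold and 10-fold differences in related studies, so it does not treat power as marginal. Those are ratios of the marker and do not convert to d without a standard deviation, so they do not settle the matter.

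Finally, the SAP has not fixed a primary model, which is the more basic gap, and the calculations above do not cover a generalized linear model with a non-linear link. Both are fair limits; the remedy can still be worded to attach to whichever model is chosen.

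**Conclusion.** The concern holds, as a minor efficiency point. The trial randomises on body fat, records it, and then names no analysis that uses it. To the extent that body fat predicts the outcome analysed, the unadjusted model-based contrasts are conservative: at an assumed R² of 0.10 the ANCOVA's true level is 0.020 against a nominal 0.025, about three points of power are lost, and the adjusted interval would be 4.5% narrower. At 0.20 the loss is about seven points and the adjusted interval would be 10.3% narrower. If body fat is unrelated to the outcome, the omission costs nothing.

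The SAP's d = 1.336 for 80% power stands for the plain two-group test. The sizes above depend on the assumed R², stratum shares, pre-loading slope and linear effect. The direction agrees with the closed-form check, which uses stratum indicators instead of a continuous term.

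**What to change.** Add one sentence to the SAP, fixed before data are seen, entering measured body-fat percentage as one continuous term in the chosen model-based group contrast:

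- **ANCOVA:** beside the pre-loading value.
- **Change score:** as the one added term.
- **Group × Time ANOVA, GEE or mixed model:** as body fat × time, because a body-fat main effect alone leaves the group-by-time result unchanged.
- **Mann-Whitney:** no requirement. Adjustment there costs about three points of power (0.741 to 0.712) if body fat is unrelated, and gains clearly only above an R² of about 0.10.

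A continuous term avoids estimating effects for sparsely filled strata. No new data are needed. The cost is one residual degree of freedom (ANCOVA 21 to 20, change score 22 to 21) and, if body fat turns out to be irrelevant, about one point of power and an interval about 1% wider. Settling it in advance also keeps the choice of covariate from depending on the results.

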Skin Moisture. We will also use a noninvasive probe to measure the amount of moisture in the skin on the lower back/sacrum. Two components of skin moisture will be measured: 1) Epidermal moisture, which reflects perspiration and 2) subepidermal moisture using a Delfin MoistureMeter D (Delfin Technologies, LTD, Grennwich, CT) dermal phase meter (http://www.delfintech.com/en/product_information/moisturemeterd/). Epidermal moisture (stratum corneum) will be measured at 0.5 mm below the skin surface and subepidermal moisture (i.e., below the epidermal stratum corneum layer) will be measured at a depth of 2.5 mm. The device consists of a control unit (signal producer) and a probe (open-ended coaxial transmission line), which is placed in contact with the skin The skin moisture will be measured at a standardized site, mid-sacrum, approximately 2 cm above the gluteal fold (avoiding the sites of the Sebutape). This location will be marked with ink pen to assure the same location for repeat measurement. For each depth, the probe will be placed on the skin surface and held for 5 seconds.

After these measurements are complete, subjects in the Mepilex dressing groups will have the dressing placed on their lower back/buttocks. All subjects will then complete an additional 5 minutes in the side-lying position, after which they will lie on their back on the designated surface. After positioning a sheet will be placed over the subject for comfort. A pillow may be placed under the head and heels at the subject's discretion.

The skin interface pressure will be measured continuously during the loaded period using the XSensor™ System (Crown Therapeutics, Belleville IL) with X3 Medical v6.0 software. This pad, which is similar to a sheet, will be positioned on the surface. *Peak skin-interface pressure*, which is the highest measured pressure for each body region and the *Peak Pressure Index* (PPI), which is the average of a 3 x 3 sensor area representing the highest pressure (including the peak pressure cell). The sacrum/buttocks will be divided into four quadrants based on the vertebral column and top of the gluteal cleft.⁵⁵ For the Mepilex groups, the pressure on the surface of the Mepilex will be recorded. Although this procedure does not directly measure skin interface pressure, which may be decreased by the Mepilex, it is not possible to place the pressure mat between the Mepilex and the skin.

Unique Procedures by Study Group

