For all groups the stretcher is placed on the bedframe of a standard hospital bed. The stretcher is secured to the bed frame. This elevation on the bedframe is for ease of access for the subjects. The bedframe is in the low position, such that the subjects will be approximately 2-3 feet off the floor.

Aeromedical Evacuation (AE) conditions

Group 1: Mepilex: Litter + AE mattress + 30° backrest elevation. Subjects will be positioned supine on the litter plus AE mattress. Mepilex will be placed on sacrum/buttocks region. Subjects will be asked to lie supine with

limited motion for 120 minutes. After completion of the 120-minute supine period, subject will be positioned side-lying. After 5 minutes side-lying, the Mepilex will be removed and the skin moisture and skin cytokine measurements will be obtained. After completion of the 15-minute side-lying phase, the skin sensors will be removed, and the study will be complete

Group 2: Without Mepilex: Litter + AE mattress + 30° backrest. Subjects will be positioned supine on the litter plus AE mattress. Subjects will be asked to lie supine with limited motion for 120 minutes. No Mepilex will be used. After completion of the 120-minute supine period, subject will be positioned side-lying. After 5 minutes side-lying the skin moisture and skin cytokine measurements will be obtained. After completion of the 15-minute side-lying phase, the skin sensors will be removed, and the study will be complete

AE Conditions with Vacuum Spine Board

Subjects in Groups 3 and 4 will be positioned on the vacuum spine board (VSB), which will be place on top of the litter + AE mattress. The litter will be elevated to 30 degrees (consistent with current practice). The vacuum will be applied according to manufacturer's recommendations. After creation of the vacuum, the VSB will be loosened around the head and feet to allow for movement for comfort. These steps do not interfere with the thoracolumbar stabilization or the interface pressure over the sacrum/buttocks. To simulate en-route care the vacuum will be maintained for 30 minutes (simulate movement to the aircraft). At 30 minutes, the

vacuum will be released with the straps in place (simulate current en route practice). At 90 minutes, the vacuum will be reapplied for 30 minutes to simulate descent and landing phase of flight (total time 120 minutes).

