The VSB straps will be in place but loosened (the photo shows the straps tightened – as they would be during transport). The subject's arms will be free (the additional litter straps – seen as olive green in the photo across the upper legs and chest will not be used). The straps will remain clipped to enhance stability of the VSB, but the subject will be able to move their arms and legs and release the straps if so desired.

Group 3: Mepilex: Vacuum Spine Board (VSB) placed on litter + AE mattress. Subject will complete above procedure. Mepilex will be placed on sacrum/buttocks before positioning on VSB. After completion of the 120-minute supine period, the vacuum will be released, and the subject will be positioned side-lying. After 5 minutes side-lying, the Mepilex will be removed and the skin moisture and skin cytokine measurements will be obtained. After completion of the 15-minute side-lying phase, the skin sensors will be removed, and the study will be complete.

Group 4: Without Mepilex: Vacuum Spine Board (VSB) placed on litter + AE mattress: Subject will complete above procedure. No Mepilex. After completion of the 120-minute supine period, the vacuum will be released, and the subject will be positioned side-lying. After 5 minutes side-lying, the skin moisture and skin cytokine measurements will be obtained. After completion of the 15-minute side-lying phase, the skin sensors will be removed, and the study will be complete

Prolonged Field Care (PFC) conditions

Subjects in the prolonged field care groups (Groups 5 and 6) will lie on the Talon litter supine (no mattress/no head of bed elevation). Pillows may be placed under the head/heels for comfort. Subjects will be asked to remain as still as possible during the 120-minute supine period. Upon completion of the supine period, subjects will be positioned side-lying for 15 minutes. Skin moisture and skin cytokine measurements will be obtained 5 minutes after the subject is positioned side-lying. After completion of the 15-minute side-lying phase, the skin sensors will be removed, and the study will be complete

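### Does leaving Mepilex on for the first 5 minutes off load spoil the skin-moisture comparison with undressed controls?

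*Protocol*

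**What the plan says.** Group numbers here follow Protocol section 5.1; the table in section 2.7 swaps Groups 1 and 2.

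- **Mepilex groups (1 and 3).** After 120 minutes supine the subject is turned on the side. "After 5 minutes side-lying, the Mepilex will be removed and the skin moisture and skin cytokine measurements will be obtained".
- **Litter control (Group 2).** "After 5 minutes side-lying the skin moisture and skin cytokine measurements will be obtained".
- **Vacuum spine board control (Group 4).** "After 5 minutes side-lying, the skin moisture and skin cytokine measurements will be obtained".
- **Baseline.** Moisture is read before any dressing goes on: "After these measurements are complete, subjects in the Mepilex dressing groups will have the dressing placed on their lower back/buttocks".
- **Method.** Two depths are read at mid-sacrum, 0.5 mm and 2.5 mm; the protocol links the shallow one to perspiration. "For each depth, the probe will be placed on the skin surface and held for 5 seconds". "This location will be marked with ink pen to assure the same location for repeat measurement".
- **Purpose.** Aim 1 (section 1.5) names moisture among its outcomes: "skin temperature and moisture and pressure between the support surface and the skin". The SAP lists it among variables "potentially reflecting the modified effects of pressure, shear and microclimate associated with lying for an interval of (120 minutes" on the support surface.
- **Status.** The SAP defines its second sample as one taken after the 120-minute load. It bases sample size on the IL-1α/total protein ratio alone and treats moisture as secondary and descriptive.

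**The concern.** Two clocks run at the post-load reading: time since the load came off, and time since then without a dressing. The protocol matches the first between arms and not the second. The 0.5 mm reading is the one most open to surface drying. If control skin dries during its 5 undressed minutes and dressed skin does not, the Mepilex arm can read moister even when the two arms were equally moist under load.

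None of the SAP's analysis options can separate these. Repeated-measures ANOVA, ANCOVA, a change score, GEE and a mixed model all use one value before and one after, and the value before is undressed in both arms. It says nothing about the 5 minutes in question.

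At stake is whether a moisture difference could be reported as the dressing altering the skin's microclimate under load when part of it came from the measurement schedule. The question concerns only the 0.5 mm contrast in the four aeromedical groups. It does not reach IL-1α/total protein, the 2.5 mm reading or the LiquiCell groups.

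**Working it through.** **The plan's own figure.** The SAP's only computed figure is a minimum d of 1.336 (12 per group, two-sided alpha 0.025, power 0.80). A two-sample t-test with the noncentral t on 22 df gives 1.3360, so it reproduces. It concerns IL-1α/total protein and does not depend on moisture timing.

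**The two clocks.** From section 5.1, taking removal as immediate and moisture as read first; minute 10 is a hypothetical repeat.

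| Reading | Minutes off load | Off-load minutes without Mepilex |
|---|---|---|
| Mepilex, minute 5 | 5 | about 0 |
| Control, minute 5 | 5 | 5 |
| Mepilex, minute 10 | 10 | 5 |
| Control, minute 10 | 10 | 10 |

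Two qualifications apply. Section 5.1 does not give the post-load order of tape and probe, and at baseline it describes tape first. If that order is kept, the Mepilex site has been undressed for at least 1 minute when the probe is applied, but the gap between arms is still 5 minutes. Also, *without Mepilex* does not mean bare: subjects wear scrubs and undergarments, and coverage of the site in those minutes is not stated.

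**How large could the bias be?** The documents give no drying rate, moisture SD or expected effect, so this is illustration only. Assume both arms carry the same excess moisture at the end of loading, and only the control site loses any. The fraction kept after 5 minutes is 0.5^(5/half-life):

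| Assumed half-life (min) | 2 | 5 | 10 | 20 | 60 |
|---|---|---|---|---|---|
| Fraction kept | 0.18 | 0.50 | 0.71 | 0.84 | 0.94 |

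If the shared excess is 1 SD, the spurious d equals the fraction lost. The chance of two-sided p < 0.05 with 12 v 12 (noncentral t, 22 df, noncentrality d × √(12/2)) is:

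| Fraction lost | 0.05 | 0.20 | 0.50 | 0.80 |
|---|---|---|---|---|
| Spurious d | 0.05 | 0.20 | 0.50 | 0.80 |
| Chance of p < 0.05 | 5% | 8% | 22% | 47% |

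The range runs from nothing to material, and the documents do not narrow it.

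**Would a repeat at minute 10 settle it?** It would probably fit. The first reading takes 2 × 5 s and ends at 5:10. Four 1-minute tapes end at 6:10 if placed together or 9:10 if placed in turn, leaving 230 s or 50 s before handling time. The repeat would end at 10:10, with 290 s of the 15-minute phase left.

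Its precision is poor. Let ρ be the assumed within-subject correlation. The 95% half-width, in SD units, for the between-arm difference in minute 5–10 change is t × √(2(1−ρ)) × √(2/n):

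| | ρ = 0.7 | ρ = 0.8 | ρ = 0.9 |
|---|---|---|---|
| 12 v 12, t(22) = 2.074 | 0.66 | 0.54 | 0.38 |
| 24 v 24, t(44) = 2.015 | 0.45 | 0.37 | 0.26 |

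A single-time contrast with 12 v 12 has half-width 2.074 × √(2/12) = 0.85 SD. These figures measure the precision of the extra analysis, not the bias.

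The repeat also fails on logic. At minute 10 the arms still differ, 5 undressed minutes against 10. Comparing Mepilex at minute 10 with control at minute 5 roughly equalises undressed time but makes time off load unequal (10 v 5). The change from minute 5 to 10 mixes drying with recovery from load. No available contrast matches both clocks.

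**The case for a change.** The best case for a change is that it is nearly free. Two 5-second probe holds in each of 48 subjects (96 readings), on a site already inked for repeat use, need no longer session. They would show whether a Mepilex–control difference persists after the dressing comes off, which the planned data cannot. The protocol also admits that interface pressure is recorded on the dressing surface and not at the skin, and makes no matching remark about moisture.

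The diagnosis stands: one post-load reading cannot separate moisture built up under load from unequal time without a dressing, and no model choice repairs that. The remedy is weaker. The repeat informs interpretation without correcting the contrast, and follows tape placement and removal that may themselves affect drying. Moving the probe ahead of the tape only after loading could also create an order difference from baseline.

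Taking the dressing off at minute 0 would match both clocks. It would also let moisture held under the dressing escape for 5 minutes before it is read. That is a different quantity and no closer to the loaded state, so the protocol's choice is a fair trade-off.

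**Conclusion.** No change to the plan is needed. The timing difference is real: 5 off-load minutes without Mepilex in controls against about 0 in the dressed arms, assuming immediate removal and moisture read first. The planned contrast is still a valid randomized comparison at equal time off load. It describes moisture at dressing removal, and should not by itself be read as the dressing's effect under load.

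That limit falls on one depth of one descriptive secondary variable. The primary endpoint, its power and the sample size do not depend on it. The SAP claims only that its variables may reflect microclimate, and places the second sample after loading. Any reading 5 minutes after unloading, in any of the six groups, falls short of moisture under load; only the unequal part belongs to the dressing schedule. That part is of unknown size and may be negligible.

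An analyst would reasonably note removal and reading times, keep tape and probe in the same order before and after loading, and describe the result as moisture at dressing removal. This is ordinary conduct and reporting. The optional minute-10 reading is something reasonable statisticians could decline.
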